Précis: Alcohol use disorder (AUD) is characterized by problematic drinking that becomes severe (NIAAA, 2017). The prevalence of insomnia in individuals with alcohol dependence is estimated to be between 36-91% and after two weeks of alcohol detoxification, as many as 65% of these individuals still experience “sleep problems.” Cognitive behavioral therapy for insomnia (CBT-I) is an efficacious non-pharmacological treatment for insomnia (Morin, et al., 2006) and is recommended as a first-line treatment for adults with chronic insomnia disorder (Qaseem, Kansagara, Forcica, Cooke, Denberg et al., 2016). CBT-I has been associated with more rapid and “durable” improvement in sleep outcomes, even when compared with other nonpharmacological treatments (Garland et al., 2014). Internet-based CBT-I (ICBT-I or eCBT-I for “electronic”) could play a key role in the dissemination of this behavioral sleep intervention, given the paucity of trained clinicians able to provide CBT-I in person and other logistical/cost concerns. SHUTi (Sleep Healthy Using The Internet) is the most tested and empirically-sound internet intervention for insomnia. The SHUTi program tailors specific recommendations based on participant responses to sleep diaries and other input within the program. Despite the promise of internet-based CBT-I interventions, very little is known about their effectiveness among individuals with AUD (Brooks & Wallen, 2014): to date, no RCTs exist examining the feasibility/effectiveness of an internet-based CBT-I program among individuals recovering from AUD. This is a two-phase randomized controlled trial assessing feasibility/acceptability and effectiveness of the SHUTi program for research participants at the NIH Clinical Center. Phase I will be focused on assessing feasibility and effectiveness of program delivery and data collection (n=10). Phase II will be a pilot RCT powered to examine intervention effectiveness (n=20 per group). All participants enrolled in this study will first be admitted under the screening and assessment protocol on the 1SE clinic (14-AA-0181), which includes adults over 18 years of age seeking treatment for alcohol rehabilitation. Participants for this study must also meet criteria for “mild to severe” insomnia. Individuals randomized to the intervention group will receive six sessions of the SHUTi intervention (one completed while inpatient, the rest while outpatient) and individuals randomized to the control group will receive an educational web-based program. The goals of the study are as follows: 1) assess the feasibility and acceptability of Internet-based CBT-I among individuals with AUD in recovery with insomnia (Phase I), 2) compare the efficacy of CBT-I versus control group with respect to primary and secondary outcome variables (Phase II), and 3) explore specific domains associated with improved outcomes: e.g. demographic, psychiatric, and/or drinking-related factors (Phase II). Primary outcome measures include changes in insomnia severity over time and changes in actigraphy-recorded sleep efficiency over time.

Alcohol and sleep disturbances. Alcohol use disorder (AUD) is characterized by problematic drinking that becomes severe (NIAAA, 2017). To be diagnosed with severe AUD, individuals must meet six or more of the 11 criteria outlined in the Diagnostic and Statistical Manual (current edition: DSM-5). This was referred to as “alcohol dependence” in previous versions of the DSM; thus, some researchers and clinicians still use the term “dependence.” Alcohol dependence is associated with insomnia and a myriad of other sleep-related disorders (Chakravorty, Chaudhary, Brower, 2016; Stein & Friedmann, 2005; Brower KJ, 2001). Insomnia in individuals who are alcohol-dependent who are actively drinking may aggravate existing psychosocial problems (Chaudhary, Kampman, Kranzler, Grander, & Debbarma, 2015). The prevalence of insomnia in individuals with alcohol dependence is estimated to be between 36-91% and after two weeks of alcohol detoxification, as many as 65% of these individuals still experience “sleep problems” (Chakravorty, et al., 2016). Data on insomnia in the patient population on the 1SE inpatient treatment unit at the NIH Clinical Center is not currently being collected, but the prevalence of sleep disturbance is relatively high throughout the course of treatment (Wallen & Brooks, 2014; Brooks, Wallen, et al., 2016). Pilot data from research participants on 1SE demonstrated a prevalence of sleep disturbances among an inpatient sample of individuals in recovery: 90% of participants reported sleep disturbances at baseline and sleep disturbances remain in around 50% of patients even at the end of the inpatient treatment period (Wallen, et al., 2014). Ongoing outpatient studies demonstrate that these sleep disturbances continue post-discharge (Brooks et al., 2016).

Evidence supporting Cognitive Behavioral Therapy for Insomnia (CBT-I) as a first-line treatment for insomnia. CBT-I is an efficacious non-pharmacological treatment for insomnia (Morin, et al., 2006) and is recommended as a first-line treatment for adults with chronic insomnia disorder (Qaseem et al., 2016). It is also effective for those with posttraumatic stress disorder (PTSD) and depression, which are common co-morbidities among those with AUD (Talbot et al., 2014; Siebern & Manber, 2011). While pharmacological intervention of insomnia in addition to CBT-I can produce added benefits acutely, it is recommended that medications should ultimately be discontinued for long-term outcomes during “maintenance” CBT-I (Morin et al., 2009). CBT-I has been associated with more rapid and “durable” improvement in sleep outcomes, even when compared with other non-pharmacologic treatments (Garland, et al., 2014).

Effectiveness of internet-delivered CBT-I. Internet-based CBT-I (ICBT-I or eCBT-I for “electronic”) could play a key role in the dissemination of behavioral sleep interventions, given the paucity of trained clinicians able to provide CBT-I in-person and other logistical/cost concerns. This method of delivery is of particular interest to researchers and clinicians working with individuals with alcohol use disorders (Brooks & Wallen, 2014). A recent systematic review and meta-analysis of 11 randomized controlled trials (total of 1460 participants) revealed that eCBT-I improved insomnia severity, sleep efficiency, subjective sleep quality, wake after sleep onset, sleep onset latency, total sleep time, and number of nocturnal awakenings with effect sizes comparable to face-to-face CBT-I (Zacharie, Lyby, Ritterband, O’Toole, 2015). Another meta-analysis showed that ICBT-I significantly improved comorbid anxiety and depression (Ye et al., 2015). The most recent meta-analysis of 15 studies showed improved sleep efficiency, insomnia severity, total sleep time, and depression severity that was maintained from 4-48 weeks after post-treatment assessment (Seyffert et al., 2016).

Protocol Number: 18-CC-0079

Description of Sleep Health Using the Internet (SHUTi) program for CBT-I. The SHUTi program is an automated, interactive, internet-based intervention based on well-established face-to-face CBT-I components including sleep restriction, stimulus control, sleep hygiene, cognitive restructuring, and relapse prevention. It consists of six core areas of focus that include interactive educational content and case studies about insomnia and its precipitating factors. These cores are designed to parallel traditional (in-person) CBT-I sessions and are “metered;” that is, new cores are available seven days after completion of the previous core. The program includes a variety of interactive features, including goal-setting, feedback based on user-identified symptoms, animations, quizzes, vignettes, and video-based expert explanations. SHUTi was developed based on the Model for Internet Interventions (a-Ritterband, et al., 2009). SHUTi users must fill out at least five daily sleep diaries for each core in seven days in order to access subsequent cores. Sleep diary input is crucial in the customization of the program based on individual situations.

SHUTi is considered a NSR IDE device as it is **not** being used in the indications as set forth:

- as an implant and presents a potential for serious risk to the health, safety, or welfare of a subject;
- purported or represented to be for use supporting or sustaining human life and presents a potential for serious risk to the health, safety, or welfare of a subject;
- for a use of substantial importance in diagnosing, curing, mitigating, or treating disease, or otherwise preventing impairment of human health and presents a potential for serious risk to the health, safety, or welfare of a subject; or
- Otherwise presents a potential for serious risk to the health, safety, or welfare of a subject”.

Protocol Number: 18-CC-0079

Effectiveness of SHUTi program. In adults with primary insomnia, SHUTi significantly improved insomnia severity index (ISI) scores and these improvements were sustained at a 6-month follow-up. Additionally, there were significant decreases in wake after sleep onset (WASO) and increases in sleep efficiency compared to a wait-list control group (a -Ritterband et al., 2009), with similar effects in adult cancer survivors (Ritterband et al., 2012). Evaluation of co-occurring symptoms in those trials showed that SHUTi also significantly improved psychological symptoms, mental health-related quality of life, and fatigue (Thorndike et al., 2013). More recently, researchers established long-term (one year follow-up) effectiveness in a representative sample with chronic insomnia and a range of comorbid conditions via randomized controlled trial (Ritterband et al., 2016). Finally, the program has significantly lowered depressive symptoms among those with both insomnia and depression symptoms (without major depressive disorder) compared to time- and attention-matched controls (Christensen et al., 2016).

Gap in the literature: Despite the established efficacy of CBT-I in the community and in those with AUD, very little is known about the effectiveness of this internet based CBT-I among individuals with AUD (Brooks & Wallen, 2014). To date, no RCTs exist examining the feasibility/effectiveness of an internet-based CBT-I program among individuals recovering from AUD.

1.1 Theoretical framework

This study will examine sleep-related beliefs and behaviors in the context of the Social Cognitive Theory (SCT; Bandura, 1986). Self-efficacy is perhaps the most well-established construct in the SCT and was an important predictor of sleep quality in our pilot work (Brooks et al., *Under Review*). We anticipate that the SHUTi program will directly impact personal, environmental, and behavioral factors for participants, and the theory includes all three as potential predictors of outcomes (insomnia severity and ultimately relapse).

1.2 Study Objectives:

1. *Phase I:* Assess the feasibility and acceptability of Internet-based CBT-I among individuals with AUD in recovery
2. *Phase II:* Compare the efficacy of CBT-I versus an education-only control group with respect to primary and secondary outcome variables
 - a. Primary outcome variables include: changes in insomnia severity over time, changes in actigraphy-recorded sleep efficiency over time
 - b. Secondary outcome variables include actigraphy-related (objective) variables, alcohol consumed (post-discharge), alcohol craving (post-discharge), sleep disturbance, daytime sleepiness, anxiety/depression, fatigue, self-efficacy for sleep, dysfunctional beliefs about sleep, and functional outcomes
 - c. Explore specific domains associated with improved outcomes: e.g. demographic, psychiatric, and/or drinking-related factors

2 Study design and methods

This is a two-phase study. Phase I will be focused on assessing feasibility and effectiveness of program delivery and data collection (n=10). Phase II will be a pilot RCT powered to examine intervention

Protocol Number: 18-CC-0079

effectiveness in the target population (n=20 per group). All study participants will receive a handheld tablet to access the SHUTi or education-only program.

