Insomnia Severity Index (ISI). The ISI is a seven-item global index of self-reported insomnia symptom severity. It is valid, reliable, sensitive to changes in insomnia treatment (Bastien, Vallieres, & Morin, 2001; Morin, Belleville, Belanger, & Ivers, 2011) and validated for online use (Thorndike et al., 2011). Seyffert and colleagues (2016) categorized insomnia severity by scores as follows: 0-7 = no clinically significant insomnia, 8-14 = subthreshold insomnia, 15-21 = moderate insomnia, and 22-28 = severe insomnia. Changes in the ISI over time will be a primary outcome measure. The ISI is collected within the SHUTi intervention program at the beginning of each core, but participants in both Phase I and Phase II will also complete a paper version of the ISI during the pre-, mid-point, and post-test assessments.

Daily sleep and symptom diaries. Prospectively collected sleep diaries are a proven method for assessing insomnia and track treatment effects (Carney, et al., 2012; Buysse, Ancoli-Israel, Edinger, Lichstein, & Morin, 2006) and have been used for other sleep studies among patients on 1SE (inpatient and outpatient). Participants will be asked to complete at least five out of every seven days of daily sleep and symptom diaries. These diaries will include sleep/wake times, time in bed, sleep onset latency, number and duration of awakenings, sleep quality, naps, alcohol consumption, any over-the-counter or prescription medications used to help with sleep (participants will be instructed to include any marijuana use in this section), and open-ended comments. For the experimental group, diaries will be used to assess adherence to their “sleep window,” based on actual time in bed as a proportion of prescribed time in bed. We will cross-validate diary-reported sleep duration with actigraphy data when possible. Secondary outcome measures captured in the diaries will include a categorical measure of relapse (i.e. whether the participant reports any drinking post-discharge) as well as quantity and frequency of drinking, which will be calculated in the case of relapse, as well as all other diary variables.

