Objective measure of sleep: actigraphy. "Actiwatches" are small wristband data loggers that record digitally-integrated measures of gross motor activity. These devices contain accelerometers and light sensors in order to objectively assess sleep. Prior studies have demonstrated actigraphy's high sensitivity with moderate accuracy for detecting sleep in populations with normal and disturbed sleep when compared to polysomnography (Kushida et al., 2001; Paquet et al., 2007). The *Actiwatch Spectrum Plus* (Philips Respironics) has been used in previous studies with patients on 1SE in both inpatient and outpatient settings. The watch is worn on the non-dominant wrist. Study participants will be asked to wear an actiwatch for 4 days, 3 nights (Phase I only) and for at least 1 week (Phase II only) at three study time points (Pre SHUT-i®/Education-Only initiation, 3-4 weeks after SHUT-i®/Education-Only initiation and Post SHUT-i®/Education-Only program completion). Participants will return the actiwatches either in person (if the participant will be returning to the Clinical Center) or by mail after each study time point so that the research team can download the data and return the watch to the participant (with the exception of the last study time point). The main outcome of interest will be improvements in sleep efficiency from baseline to follow-up assessment periods. The watch also provides measures of total sleep time (TST), wake after sleep onset (WASO), sleep onset latency (SOL), number of awakenings (NWAK), and time in bed (TIB).

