Any experimental pharmacological agent may affect the data collected for this study and its effect on sleep will be largely unknown. As a result, our research team decided on excluding participants that are enrolled in any experimental pharmacological study.

PI Name: [name]

Version Date: 12/07/2020

Protocol Number: 18-CC-0079

Study measures have only been validated in English.

Additional note: after enrollment in the study, the management of sedatives/hypnotics for individuals who have been prescribed either will be done by a clinician who is blind to the treatment condition.

Protocol Number: 18-CC-0079

3 Statistical analysis:

Qualitative analysis (Phase I participants only). Each audio-recorded interview will be transcribed verbatim. A codebook will be developed based on themes from the interviews. Each code will be accompanied by an operational definition that will allow for clarity and consistency in the coding process. Evidence of each code or theme will be assessed using quotes from the interviews. A team of coders will independently review all transcripts. Discordant coding will be discussed until consensus among the coding team is achieved. Once the iterative process of consensus building is complete, an intramural expert in qualitative methodology will validate the final themes and coding. After data are coded, NVivo will be utilized for further qualitative analysis and data management.

Quantitative analyses (Phase II only). The first step in quantitative data analysis will be running baseline "diagnostics" to check for outliers and normal distribution of all continuous variables. If the assumptions of normality are not violated, we will proceed with parametric testing. If the assumptions of normality are violated, non-parametric tests will be utilized. For quantitative analyses, statistical significance will be considered at $p < 0.05$.

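### Two unranked primary outcomes are listed, but the statistics section powers and models only insomnia severity, with no multiplicity rule and no named deciding contrast

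*Combined protocol and SAP*

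**What the plan says.** Where the primary outcomes are named:

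- Précis: "Primary outcome measures include changes in insomnia severity over time and changes in actigraphy-recorded sleep efficiency over time".
- Section 1.2, item 2a: "Primary outcome variables include: changes in insomnia severity over time, changes in actigraphy-recorded sleep efficiency over time".
- Section 2.4, ISI paragraph: "Changes in the ISI over time will be a primary outcome measure". The indefinite article fits there being more than one.
- Section 2.4, actigraphy paragraph: "The main outcome of interest will be improvements in sleep efficiency from baseline to follow-up assessment periods".
- Section 1.2, item 2b: "Secondary outcome variables include actigraphy-related (objective) variables", followed by a list of other measures.

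Where they are analysed (section 3):

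- The Phase II sample-size paragraph speaks of primary hypotheses in the plural. It then takes insomnia severity as the primary outcome, with a two-sided hypothesis that its rate of change differs between groups.
- That paragraph assumes a correlation of 0.6 between two unnamed time points, alpha 0.05, power 0.8 and 40% attrition, and gives a detectable effect of 0.84 with 60 participants.
- The mixed model with group, time and their interaction is specified for insomnia severity. The next sentence extends mixed models to the secondary objectives. Sleep efficiency as a primary outcome appears in neither sentence.
- On the threshold: "For quantitative analyses, statistical significance will be considered at" p < 0.05. No testing order, alpha split or both-required rule is given.

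On timing, section 2.4 has participants complete a "paper version of the ISI during the pre-, mid-point, and post-test assessments", and the Table of Measures also marks the ISI at 6–7 months post-discharge. I put no weight on marks that seem to be absent elsewhere in that row, because the table may not have been read intact.

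**The concern.** The objectives and the statistics section disagree about how many primary outcomes there are. A self-reported score and a wrist-worn device can give different answers. On the text as it stands, a result on ISI alone or on sleep efficiency alone could each be presented as meeting a primary outcome, and the choice could be made once results are known. The stated power covers only one of the two.

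A second gap lies inside the ISI analysis. Power is computed for two time points, but the ISI is collected at three or more. An interaction test over several visits is not the same test as a pre-to-post contrast, and the two can differ in power and in conclusion.

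The pilot label lowers the stakes without removing them, since the précis also says: "Phase II will be a pilot RCT powered to examine intervention effectiveness (n=20 per group".

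**Working it through.** **1. The plan's own figure.** Inputs from section 3: N = 60, attrition 40%, correlation 0.6, two-sided alpha 0.05, power 0.80.

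- Completers: 60 × 0.6 = 36, or 18 per arm.
- SD of change, in units of the outcome SD: √(2 × (1 − 0.6)) = 0.894.
- Detectable effect: (1.960 + 0.842) × 0.894 × √(2/18) = 0.835, against the stated 0.84.
- Power at 0.84: standard error = √(1.6/18) = 0.298; Φ(0.84/0.298 − 1.96) = 0.804.

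The figure reproduces by a normal approximation as a two-time-point comparison of change in ISI. With the 20 per group quoted in the précis, power at 0.84 is 0.844.

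**2. Family-wise error under each reading of success.** Two tests, each two-sided at 0.05, both nulls true, statistics assumed jointly normal. The documents give no correlation between the outcomes, so a range is shown. If either outcome suffices, the error is 1 − P(|Z₁| < 1.96, |Z₂| < 1.96):

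| Assumed correlation | Family-wise error |
|---|---|
| 0 | 1 − 0.95² = 9.75% |
| 0.5 | 9.1% |
| 0.7 | 8.4% |
| 0.9 | 7.0% |
| Bound for any dependence | 10% |

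If ISI alone decides, or both outcomes must succeed, the error is at most 5%.

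**3. Which ISI contrast.** Take 18 per arm, a post-test effect of 0.84, and an assumed correlation of 0.6 between every pair of visits (compound symmetry).

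- Pre-to-post contrast, 1 df: 80.4%, as in step 1.
- Linear trend over equally spaced pre, mid and post visits: the mid-point has weight zero, so the slope is half the pre-to-post change and power is again 80.4%.
- Interaction with time as categories, 2 df: with m the group difference in change at mid-point and p = 0.84 at post-test, the covariance matrix of the two differences is (2/18) × [[0.8, 0.4], [0.4, 0.8]], so the noncentrality is 15(m² − mp + p²).

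| m | Noncentrality | Power |
|---|---|---|
| 0 | 10.58 | 84% |
| 0.21 | 8.60 | 75% |
| 0.42 | 7.94 | 71% |
| 0.63 | 8.60 | 75% |
| 0.84 | 10.58 | 84% |

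The 71% is the minimum, reached when the mid-point effect is exactly half the post-test effect. The calculation leaves out the 6–7 month visit; the plan does not say whether that visit enters the model.

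**4. Cost of keeping two primaries with a Bonferroni split.** At alpha 0.025, ISI power at 0.84 is Φ(0.84/0.298 − 2.241) = 0.718 with 18 per arm. Restoring 80% takes 22 completers per arm, and 44/0.6 = 73.3, so 74 randomised.

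**5. Sleep efficiency.** The power paragraph cites d = 0.68 from one earlier study without saying whether it is actigraphy-based or a between-group effect. Taken as a between-group effect in raw SD units, with 18 per arm at 0.05, power runs from 46% at an assumed pre–post correlation of 0.4 to 90% at 0.8. That spread is too wide to support any single figure.

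**The case against.** The strongest reply is that section 3 already settles the matter. It calls insomnia severity the primary outcome with a definite article, gives it the full alpha, and names no other outcome in the main model. On the natural reading, the statistics section does designate ISI. This stands, so it would be wrong to say that the plan nowhere identifies a primary outcome. But the designation is a premise of the sample-size calculation. It does not withdraw sleep efficiency from the primary list in the précis and section 1.2, and the conflict remains.

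Two other passages look like further contradictions but are not. The actigraphy paragraph's main outcome ranks sleep efficiency above the watch's other measures, such as total sleep time and wake after sleep onset; it does not set it against ISI. Item 2b of section 1.2 follows directly on 2a, so its actigraphy variables are most simply read as the remaining ones.

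It is also fair to say that a hypothesis about rate of change, tested by group-by-time, need not name a single deciding visit. That answers part of the timing question. It does not say whether time is linear or categorical, which visits are included, or whether the decision rests on one contrast or a joint test.

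Finally, a reader might infer that the trial runs at nearly 10% type I error. No passage says that either outcome suffices; none rules it out. The 9.75% is conditional on that reading.

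**Conclusion.** The point holds as a conflict between the stated objectives and the statistics section, with two consequences.

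- **Outcome.** Error is up to 9.75% under independence (10% as a general bound) if either listed primary may be claimed, and at most 5% otherwise. The intermediate values assume jointly normal statistics and correlations that the documents do not supply.
- **Contrast.** Power at 0.84 is 80% for a pre-to-post contrast or an equally spaced linear trend, and 71–84% for a three-visit 2-df interaction as the mid-point effect ranges from zero to the full post-test effect. This assumes compound symmetry at 0.6 and 18 completers per arm.

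A reader might also infer that the sample size is wrong or that the ISI test is underpowered. The documents do not support either: 60 participants and 0.84 reproduce, and 71% is only the lowest value under one possible test. Nor can the trial be called underpowered for sleep efficiency, because the plan gives no basis for a figure.

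Because Phase II is a pilot, this is at most a change that should be made, not one on which the trial's validity turns.

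**What to change.** Reconcile the précis, section 1.2 and the ISI paragraph of section 2.4 with section 3, before outcome data are examined:

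1. Name change in ISI from pre-test to post-test as the single primary outcome, tested by the 1-df group-by-time contrast from the mixed model at two-sided 0.05. Make the primary hypothesis singular in section 3.
2. State which ISI visits enter the model, including whether the 6–7 month assessment does.
3. Test pre-to-post change in actigraphy sleep efficiency next, with the same contrast at two-sided 0.05, only if the ISI test is significant. Otherwise report its estimate and 95% confidence interval as exploratory.
4. State that 80% power at 0.84 with 60 participants applies to ISI only, and give no power figure for sleep efficiency.

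The cost is a few sentences. The sample size and planned ISI power are unchanged. The downside is that sleep efficiency, which the sponsor twice lists as primary, cannot be claimed as confirmatory if ISI fails. Fixing pre- and post-test as the two time points is also a choice, since section 3 does not name them.

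If the sponsor prefers two primaries, the plan should state the rule and its price. A Bonferroni split lowers ISI power at 0.84 from 80% to 72% at 18 completers per arm. Requiring both needs no alpha adjustment, but joint power cannot exceed the 80% for ISI and depends on a sleep-efficiency power that the documents do not establish.
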